Despite the growing data about the potential advantages of the use of FC in adult cardiac surgery patients, it is not yet known, however, whether the use of FC in pediatric cardiac surgery patients may offer similar advantages. A recent prospective randomized study by Downey et al compared the use of FC to cryoprecipitate in pediatric patients undergoing cardiac surgery. Although there was no difference in postoperative bleeding between the study groups, children in the FC group received significantly less allogeneic blood products compared to patients who received cryoprecipitate. Some of the patients, however, also received prothrombin complex concentrate – a potent mixture of vitamin K-dependent clotting factors, which may complicate the interpretation of the results. Furthermore, the standard of care at the UVA Medical Center, as well as in other pediatric cardiac surgery institutions, is to prime the cardiopulmonary bypass pump only with RBCs without adding FFP (which is different than in the Downey paper). This results in a much more significant hemodilution that may lead to a higher risk of postoperative bleeding.

Taken together, there is a growing body of evidence supporting the use of fibrinogen concentrate as an alternative for cryoprecipitate in adult cardiac surgery patients, however, there is insufficient data in the literature to determine whether FC may be a comparable (or even a superior) alternative to cryoprecipitate for fibrinogen supplementation after pediatric cardiac surgery. Therefore, we propose a single-institution, prospective randomized pilot study to compare the use of FC (Fibryga, Octapharma USA, Hoboken, NJ, USA) to cryoprecipitate in pediatric cardiac surgery patients with postoperative bleeding and low fibrinogen levels. If FC is found to offer similar hemostatic efficacy as cryoprecipitate it may be a much better alternative for fibrinogen supplementation in bleeding pediatric cardiac surgery patients given its higher safety profile.

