### Objectives/Hypothesis

#### INSTRUCTIONS:

If this study involves biomedical research clearly state the objectives and hypotheses and clearly define the primary and any secondary outcome measures. If this study involves qualitative research clearly state your research hypothesis or question.

This section should not include information already included in other sections such as background information or information from the procedures section.

Answer/Response: Our hypothesis is that fibrinogen concentrate will be as effective as cryoprecipitate in achieving adequate hemostasis after separation from CPB in pediatric cardiac surgery patients.

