### **4. What is your plan for primary variable analysis?**

Include primary outcome(s)/predictor variable(s), statistical methods/models/tests to be employed, or descriptive summaries as appropriate. If not applicable, please provide explanation.

Answer/Response:

Outcomes: the primary outcome of the study will be any allogeneic blood transfusion within the first 24 hours after administration of the FC or cryoprecipitate.

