### **5. What is your plan for secondary variable analysis?**

Include the following:  
--Secondary outcome(s)/predictor variables, statistical methods/models/tests to be employed, or descriptive summaries as appropriate. If not applicable, please provide explanation.  
--For phase III studies, the power/precision of the study to address the secondary objective(s).

Answer/Response: Secondary outcomes will include: administration of individual blood products (RBC, platelets, FFP, cryoprecipitate) over the initial postoperative 48 hours and up to 7 days after surgery, bleeding over the first postoperative 48 hours (intraoperatively = cell saver volume; postoperatively = chest drain/s output), the need for surgical re-exploration for hemostasis over the first postoperative 48 hours, the use of recombinant factor VIIa as rescue for refractory bleeding in the first 48 postoperative hours, length of ICU stay, hospital length of stay, thromboembolic complications over the first seven postoperative days and a 30-day composite of AKI, stroke, severe myocardial dysfunction or myocardial infarction, sepsis and

mortality (or until discharge whichever is earlier).

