In the event that a second round of fibrinogen supplementation is required (bleeding with documented hypofibrinogenemia) participants will receive either FC or cryoprecipitate based on their initial randomization. If any additional fibrinogen supplementation is then needed (after the first 2 supplementation doses), cryoprecipitate will be administered to all subjects per standard of care (including those who received FC).

Data to be obtained:

1. Demographic/preoperative data: collected from the medical record
  - age in days/months (all patients to be younger than 24 months)
  - gender
  - weight
  - preoperative diagnosis
  - surgery type & date (Norwood, arterial switch, truncus arteriosus, Glenn, Fontan, TAPVR, AV canal, tetralogy of Fallot, etc)
  - preoperative standard of care labs PT/aPTT/INR/hgb level/ hematocrit/ platelet count/

fibrinogen level (if exists)/ creatinine

2. Intra-operative Data: collected from the medical record

- CPB time & aortic cross clamp time
- use of hypothermic circulatory arrest (ice packs placed on the head)
- was post-CPB ultrafiltration performed?
- Platelet count prior to separation from CPB
- was ATIII administered? (thrombate)
- Transfusion requirements: PRBC/Cell Saver/FFP/PLT/ cryo - to be collected as number of units per each product, not volume. (for PLT - was it pooled PLT or single donor apheresis, if possible)
- was rFVIIa given (factor seven, novoseven). Please pay attention - the fact that rFVIIa was ordered DOES NOT mean that was actually administered as we order factor VII for ALL big cases (to have available in the OR) but not necessarily administer it
- Need for ECMO
- Was the chest left open? (always in ECMO, but open chest does not necessarily mean ECMO)

ROTEM (clotting labs) will be drawn for research purposes after admission and after administration of the study treatment: Extem (CT/A10/A20/MCF); Fibtem (A10/A20/MCF) and fibrinogen. The blood drawn for this will be obtained through an existing line, put into place as part of the subject's usual care.

3. Postoperative Data (PICU, up to 48 hours after surgery) collected from the medical record

- admission PT/aPTT/INR/platelet count/ fibrinogen level/ hgb level/HCT level (could be obtained from initial ABG)
- Bleeding (Chest drain/s output)

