- Need for additional transfusion (PRBC/cell saver/FFP/platelets/cryoprecipitate). Will need to know, if possible, whether transfused from same unit that was already exposed to in the OR or new unit (= new exposure)
- Factor VIIa administration
- re-exploration? (= starting ECMO in the PICU)
- delayed chest closure? (will answer whether went to PICU with chest open)

**2. If this protocol involves study treatment, explain how a subject will be transitioned from study treatment when they have completed their participation in the study.**

**Example:** If the subject will be taking an investigational drug, will they need to be put back on an approved drug when they have completed the study? If yes, explain how this will be accomplished and who will cover the cost. If the subject has a device implanted will it be removed? Again- who will cover the cost of the removal?

**Instructions:** Answer NA if this study does not involve a study treatment.

Answer/Response: There is no transition from study treatment.

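### The primary outcome does not exclude study-assigned cryoprecipitate, so a second fibrinogen dose within 24 hours is an event in the control arm but not in the FC arm

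*Combined protocol and SAP*

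**What the plan says.** Statistical Considerations, question 4, defines the primary outcome as "any allogeneic blood transfusion within the first 24 hours after administration of the FC or cryoprecipitate". It gives no product list and no exclusion for the randomised product.

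The protocol treats cryoprecipitate as a blood product in three places:

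- Statistical Considerations, question 5, has as a secondary outcome "administration of individual blood products (RBC, platelets, FFP, cryoprecipitate) over the initial postoperative 48 hours".
- Study Procedures, question 1, intra-operative data: "Transfusion requirements: PRBC/Cell Saver/FFP/PLT/ cryo - to be collected as number of units per each product, not volume".
- Study Procedures, question 1, postoperative data: "Need for additional transfusion (PRBC/cell saver/FFP/platelets/cryoprecipitate").

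FC is on none of these lists. The Background also sets FC apart from such products: it reports of an earlier pediatric trial that "children in the FC group received significantly less allogeneic blood products compared to patients who received cryoprecipitate".

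Study Procedures, question 1, fixes what is given when more fibrinogen is needed. At the second round, "participants will receive either FC or cryoprecipitate based on their initial randomization". After two doses, "cryoprecipitate will be administered to all subjects per standard of care (including those who received FC"). The hypothesis (Objectives/Hypothesis) is that "fibrinogen concentrate will be as effective as cryoprecipitate in achieving adequate hemostasis after separation from CPB".

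**The concern.** Read together, these rules make the outcome depend on the name of the product as well as on the infant's course. Take two infants who both still bleed with low fibrinogen some hours after the first dose and receive no other product. The control infant receives a second dose of cryoprecipitate and has a primary event. The FC infant receives a second dose of FC and has none. Hemostasis failed equally in both.

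The trial asks whether FC achieves hemostasis as well as cryoprecipitate. If repeat use of the comparator counts as failure in one arm only, part of any difference in favour of FC reflects the definition, and the primary analysis cannot separate that part from a real effect.

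**Working it through.** **1. Which doses score, by arm**

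| Dose | Control arm | FC arm |
|---|---|---|
| First (index) | Cryoprecipitate; before the window on the plain reading, not explicitly excluded | FC; not counted |
| Second, within 24 h | Cryoprecipitate; counted | FC; not counted |
| Third and later | Cryoprecipitate; counted | Cryoprecipitate; counted |

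The asymmetry that follows from the plan as written is confined to the second dose.

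**2. The plan's own figure**

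Statistical Considerations, question 2, gives 30 infants (15 per arm) for a difference of 2 allogeneic products, 80% power, alpha 0.05, including 20% dropout. The dropout step is consistent with 24/(1 − 0.20) = 30. The rest cannot be reproduced because no SD is given, and question 3 says that no power analysis was done. Solving for the SD that gives 80% power at a difference of 2 (two-sided t test) yields 1.67 with 12 evaluable per arm and 1.89 with 15 per arm. These SDs are back-solved and are not the plan's.

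**3. Second doses only, outcome as worded (any transfusion: yes or no)**

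Assumptions, none of them in the documents: a proportion p receives some other product within 24 h, and a proportion r needs a second dose within 24 h. Both are the same in the two arms and independent of each other. Then

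- FC-arm rate = p
- control-arm rate = p + r(1 − p)

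Example: p = 50%, r = 30% gives 0.50 + 0.30 × 0.50 = 65% against 50%, with no true difference.

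Probability that Fisher's exact test (15 per arm, two-sided 0.05) is significant in favour of FC, by enumeration:

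| p | r = 0 | r = 10% | r = 20% | r = 30% | r = 40% |
|---|---|---|---|---|---|
| 50% | 0.8% | 1.7% | 3.2% | 5.7% | 9.6% |
| 60% | 0.8% | 1.4% | 2.5% | 4.2% | 6.9% |
| 70% | 0.8% | 1.4% | 2.2% | 3.4% | 5.2% |
| 80% | 0.8% | 1.2% | 1.6% | 2.2% | 3.0% |
| 90% | 0.3% | 0.3% | 0.4% | 0.4% | 0.5% |

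Under equality (r = 0) the largest value between p = 50% and 90% is 0.9%, at p = 75%. The range with second doses counted is 0.3-9.6%. If the infants who need a second dose are mostly those who receive other products anyway, the inflation is smaller than shown.

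**4. Second doses only, count of products**

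The sizing statement is on a count, so this scale matters too. Built-in shift = r × units per second dose. With r = 10-40% and 1-2 units (assumed), the shift runs from 0.1 × 1 = 0.1 to 0.4 × 2 = 0.8 products. The upper end is 0.8/2 = 40% of the design difference. Two-sided t-test rejection, with noncentrality = shift/(SD × √(2/n)):

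| Shift | SD 1.67, 12 per arm | SD 1.89, 15 per arm |
|---|---|---|
| 0.1 | 5.2% | 5.2% |
| 0.4 | 8.7% | 8.7% |
| 0.8 | 20.2% | 20.1% |

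**5. Conditional case: only if the first dose were also counted**

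Every control infant would then have the event (15/15). Fisher's test is significant when FC has 10/15 or fewer (10/15 gives p = 0.042; 11/15 gives p = 0.100). P(X ≤ 10) for a binomial with n = 15 is 94%, 78%, 48%, 16% and 1% at true other-transfusion rates of 50%, 60%, 70%, 80% and 90%.

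**The case against.** A reader might infer that the outcome counts the control arm's first dose, so that control is 100% by definition. The documents do not support that as the plan's meaning. The window opens after administration of the study product, and the postoperative data item speaks of additional transfusion, so both point to products given after the index dose. Cryoprecipitate has its own line in the unit counts and study-drug administration is documented in the electronic record, so the index dose should be traceable. What remains is that the first dose is not excluded in so many words, and that the text does not say whether the clock starts at the beginning or the end of that dose.

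A second objection is that counting cryoprecipitate is the point. The Background is about reducing allogeneic transfusion, the sizing statement is in terms of product exposure, and the data items track new donor exposures. For a donor-exposure question, counting cryoprecipitate is the effect of interest. That is fair, but the stated hypothesis concerns hemostasis, and one primary outcome cannot answer both questions when one arm's hemostatic agent is itself an exposure.

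Third, the secondary outcomes report each product separately, so a difference due only to cryoprecipitate would show. This helps only in part, because those outcomes cover 48 hours and 7 days while the primary covers 24 hours. The pilot label does not remove the problem either: the plan tests at alpha 0.05, and a biased estimate would carry into a later trial.

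**Conclusion.** The concern holds for second doses within 24 hours. Followed as written, the plan scores the same event only in the control arm, and the direction always favours FC. This is a rule that biases the result, so it should be corrected before the outcome is analysed.

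The size is modest and uncertain. Under the assumed rates, false significance for FC on the binary outcome is about 0.3-9.6%, against 0.3-0.9% under equality, and it fades when nearly every infant receives another product. On the count scale, two-sided rejection is 5-20% against a nominal 5%, and the top value needs 40% of infants to receive two extra units each. The repeat-dose rates, other-transfusion rates, units per dose and SDs are all assumptions.

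The much larger figures (94% down to 1%) apply only if the index dose is counted, which is not the natural reading. It would also go too far to infer that a positive result would merely restate the treatment assignment.

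**What to change.** 1. Define the primary outcome as RBC, platelets and FFP given in the 24 hours from a stated start time relative to the first study-product dose. Exclude study-assigned fibrinogen product, first and second doses, in both arms.
2. Add as a secondary outcome the number of fibrinogen supplementation doses of either product, counted the same way in both arms. The third and later cryoprecipitate doses are counted there.
3. Keep total allogeneic exposure including cryoprecipitate as a labelled secondary outcome, so that the donor-exposure question is still answered.

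The cost is a change of outcome wording and one derived variable, for which study-assigned cryoprecipitate has to be told apart from other cryoprecipitate, with administration times. Treatment does not change. The downside is that the headline difference may be less favourable to FC, and donor exposure moves from the primary to a secondary outcome.

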### **5. What is your plan for secondary variable analysis?**

Include the following:  
--Secondary outcome(s)/predictor variables, statistical methods/models/tests to be employed, or descriptive summaries as appropriate. If not applicable, please provide explanation.  
--For phase III studies, the power/precision of the study to address the secondary objective(s).

Answer/Response: Secondary outcomes will include: administration of individual blood products (RBC, platelets, FFP, cryoprecipitate) over the initial postoperative 48 hours and up to 7 days after surgery, bleeding over the first postoperative 48 hours (intraoperatively = cell saver volume; postoperatively = chest drain/s output), the need for surgical re-exploration for hemostasis over the first postoperative 48 hours, the use of recombinant factor VIIa as rescue for refractory bleeding in the first 48 postoperative hours, length of ICU stay, hospital length of stay, thromboembolic complications over the first seven postoperative days and a 30-day composite of AKI, stroke, severe myocardial dysfunction or myocardial infarction, sepsis and

mortality (or until discharge whichever is earlier).

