**Study Procedures-Biomedical Research**

**1. What will be done in this protocol?**

**INSTRUCTIONS:**

This should include everything that will be done as part of this protocol. Do not repeat information that is included in other sections such as Background or Hypothesis sections.

This section should include an indication of which research interventions if any offer a prospect for direct benefit and which interventions (invasive measurements, collection of blood, tissue, data, surveys, etc.) are being done solely to answer a research question and generate generalizable knowledge. If the interventions done solely for research purposes are associated with greater than minimal risk they need to be justified.

Describe and justify any control and experimental arm and include method, dose, and duration of drug administration. Reference any claim of clinical equipoise if applicable.

If you are obtaining specimens or data, provide information regarding the type of specimen/data, amount of specimen needed and how the specimen/data will be obtained and what analysis will be done with the specimen/data.

Special note for studies with waiver of consent/waiver of documentation of consent:

Include a statement regarding how subjects will be recruited. For other studies this information is captured in Recruitment does not need to be duplicated in this section.

Answer/Response:

The parent/ legal guardian will be consented at a clinic or hospital visit prior to surgery by study staff and will include the Peds Cardiac NP they are familiar with when possible. Subjects will be monitored for 48 hours for the need for fibrinogen supplementation

Once the need for fibrinogen supplementation is confirmed in the OR or PICU, subjects will be randomized into one of two treatment groups (n=15 in each group):

1. Cryoprecipitate group (dose: 10 ml/kg; active control group) or
2. Fibrinogen Concentrate group (dose: 70 mg/kg; intervention group) single dose.

Administration of the study drug is via transfusion.

There will be no placebo group since withholding treatment is neither consistent with standard of care nor acceptable ethically.

No other aspects of care will be modified.

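### No component of the 30-day composite has a postoperative data item, and the listed postoperative capture ends at 48 hours

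*Combined protocol and SAP*

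**What the plan says.** Under Statistical Considerations, question 5, the last secondary outcome is "a 30-day composite of AKI, stroke, severe myocardial dysfunction or myocardial infarction, sepsis and" "mortality (or until discharge whichever is earlier"). The same answer includes "thromboembolic complications over the first seven postoperative days" and the administration of individual blood products "over the initial postoperative 48 hours and up to 7 days after surgery". It defines none of the composite's components.

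The data to be collected are listed under Study Procedures-Biomedical Research, question 1. Item 1 (preoperative) ends its laboratory list with "fibrinogen level (if exists)/ creatinine". Creatinine appears nowhere else. Item 3 is headed "Postoperative Data (PICU, up to 48 hours after surgery) collected from the medical record", and its laboratory line reads "admission PT/aPTT/INR/platelet count/ fibrinogen level/ hgb level/HCT level (could be obtained from initial ABG"). The rest of item 3 covers chest drain output, further transfusion, factor VIIa, re-exploration and delayed chest closure. No section describes follow-up to day 7, day 30 or discharge.

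**The concern.** An outcome can be analysed only if the plan says what is recorded for it, over what period, and how an event is recognised. Here the outcome section and the data section do not match. An abstractor who follows the list would record a baseline creatinine, stop at 48 hours, and have no field for any component of the composite.

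This matters because the composite is the only listed outcome that combines organ injury with death, and the Background names kidney injury among the complications linked to transfusion. With 15 infants per arm, a few events recorded in one chart and overlooked in another could change the picture. The trial is unblinded, and the documents do not say that abstraction or event classification is masked. If the AKI rule and the search period are chosen after the data are seen, they may be chosen or applied with knowledge of the arm.

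**Working it through.** The plan states no event rate or power for the composite, so there is no figure to reproduce. The check sets the outcomes in question 5 against the data list.

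| Outcome (question 5) | Stated window | Postoperative item in the data list |
|---|---|---|
| AKI | day 30, or discharge if earlier | none; creatinine preoperative only, no urine output or renal replacement item |
| Stroke | same | none |
| Severe myocardial dysfunction or infarction | same | none |
| Sepsis | same | none |
| Death | same | none |
| Thromboembolism | 7 days | none |
| Individual blood products | 48 hours and up to 7 days | yes, to 48 hours |

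**Components with an item.** The composite has 5 components and 0 have a postoperative item. The nearest entry is ECMO, which appears as an intraoperative item and again in the note on re-exploration. The plan does not tie it to the composite.

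**Period covered.** The listed postoperative capture is 48 hours, or 2 days. The start of the 30-day window is not stated; I assume it is surgery. With D the number of days from surgery to discharge, and D at least 2, the share of the composite's window inside the listed capture is 2 / min(30, D).

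- Infant still in hospital at day 30: 2/30 = 6.7%.
- Infant discharged on day 7 (illustration only): 2/7 = 29%.
- Seven-day outcomes: 2/7 = 29%. For transfusion this is the share actually listed. For thromboembolism it is only an upper limit, because no item exists.

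The documents give no distribution of hospital stay, so there is no single figure for the composite. Discharge date and length of stay are also absent from the list, although discharge can close the window and both ICU and hospital stay are secondary outcomes.

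**Scoring from the listed items.** A creatinine-based AKI rule compares a later value with baseline. The list supplies the baseline and no later value, so the component is missing for every infant. The other four components have no field at all. The composite built strictly from the list is therefore missing for all infants. The plan does not say that missing means no event, so an undercount does not follow.

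**The case against.** The strongest reply is that the list is not the limit of what can be known. Its clinical items come from the medical record, and the protocol leaves usual care otherwise unchanged. Postoperative creatinine, a stroke diagnosis or a death may therefore be in the chart and open to later abstraction. Because the window closes at discharge, it lies within the hospital record. The list also reads like notes to an abstractor and omits other named outcomes, such as length of stay, so it may never have been meant as a complete case report form. Finally, this is a late-listed secondary outcome in a pilot of 30 infants. The hypothesis concerns hemostasis, and the Background bases the safety advantage of fibrinogen concentrate mainly on pathogen reduction, avoidance of lung injury and smaller volume, not on this composite.

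Most of this stands, and it limits the point. A reader might infer that AKI can never be scored, or that the data will not exist. The documents support neither: they do not list postoperative creatinine, but they do not rule out abstracting it. A reader might also infer that the composite is undercounted by some calculable share through the loss of AKI. That would need event rates the documents do not give. It would also need the other four components to be fully captured, and they are no more listed than AKI is.

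The mismatch remains. The template's instruction for this section reads "This should include everything that will be done as part of this protocol", and the list is detailed elsewhere, asking for units rather than volumes and distinguishing a drug ordered from a drug given. That values may be retrievable does not supply an AKI definition, a search period or a field. It does make the repair cheap.

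**Conclusion.** The point holds as a conflict between the stated outcomes and the listed data. None of the 5 components of the composite has a postoperative item, AKI has no definition, and listed capture stops at 48 hours against a window of up to 30 days. The same conflict affects thromboembolism and transfusion to 7 days. Abstracted as listed, the composite cannot be scored. Filled in informally, it is open to missing or uneven data in an unblinded comparison.

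This rests on reading the data list as the abstraction plan, which the template instruction supports. The direction and size of any bias cannot be computed from the documents. The composite is secondary and the trial was not sized on it, so neither the primary outcome nor the sample size is affected. It should be corrected before data are abstracted.

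**What to change.** In Study Procedures, question 1:

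- Extend the postoperative chart abstraction to day 30 or discharge, whichever is earlier, for the composite, and to day 7 for thromboembolism and transfusion. State the starting point of each window and record the discharge date.
- Add the postoperative creatinine values already in the chart, with dates, and any renal replacement therapy.
- Add one dated yes/no field each for stroke, severe myocardial dysfunction or infarction, sepsis, death and thromboembolism.

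In Statistical Considerations, question 5, define the AKI endpoint as a stated change from the preoperative creatinine already collected.

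The cost is a little more abstraction time for about 30 infants, from the same record. It needs no extra blood draw, visit or patient.
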